## **9.9. Prohibited and Permitted Therapies**

All concomitant medications (including over-the-counter medications and herbal supplements) and concomitant therapies used will be recorded in the source document and on the appropriate eCRF.

No potential drug interactions or overlapping toxicities with current standard-of-care treatments for COVID-19 have been identified. In vitro cytochrome P450 enzyme interaction studies showed that varespladib would not cause clinically significant inhibition of the metabolic clearance of drugs metabolized by CYP3A (such as dexamethasone), and no effect of varespladib on p-glycoprotein.

Participants may receive supportive care according to the written standard of care policy or guidance for the trial site hospital. The written institutional standard of care at each site may change during the study.

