### **9.9.1 Prohibited Therapies**

Experimental treatment or off-label use of marketed medications intended as specific treatment for COVID-19 is prohibited from Day 1 through Day 28 unless such treatments are outlined by the institution's written standard of care. Dialysis before the study is prohibited. Prospective participants on mechanical ventilation or ECMO at the time of enrollment are not eligible, but these therapies may be started during the study.

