**Table 10-1: WHO 9-point Ordinal Scale**

Patient State	Descriptor	Score
Uninfected	No clinical or virological evidence of infection	0
Ambulatory	No limitations on activities	1
	Limitation on activities	2
Hospitalized; mild disease	No oxygen therapy	3
	Oxygen by mask or nasal prongs	4
Hospitalized; severe disease	Noninvasive ventilation or high-flow oxygen	5
	Intubation and mechanical ventilation	6
	Ventilation plus additional organ support (pressors, renal replacement therapy (RRT), extracorporeal membrane oxygenation (ECMO)	7
Dead	Death	8

The timepoints are indicated in the Schedule of Events ([Table 2-1](#)).

Endpoints pertaining to hospitalization and mortality will be assessed using these data and post-discharge eCRF questions.

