2.2.1.2. Secondary Efficacy Endpoint(s)

The secondary efficacy endpoints of this study include the following:

- Clinical improvement as measured by the World Health Organization (WHO) 9-point ordinal scale from baseline through Day 60
- Time to and proportion of participants with all-cause mortality through Day 60
- Proportion of participants who experienced respiratory failure within the first 28 days after randomization
- Among patients that never experience respiratory failure in the first 28 days, time to initiation, duration, and proportion of subjects receiving supplemental oxygen or other respiratory support within the first 28 days after randomization
- Among patients that experience respiratory failure in the first 28 days, time to initiation and duration of the forms of respiratory support meeting criteria outlined in critical COVID criteria (exclusion criteria 1.c.i) within the first 28 days after randomization
- Number of days of oxygen support through Day 28 after randomization
- SpO₂ through Day 28 after randomization

- Number of ventilator-free days through Day 28 after randomization
- Number of hospitalization days through Day 28 after randomization
- Number of days without renal stabilization and/or replacement through Day 28 after randomization
- Number of organ failure-free days through Day 28 after randomization
- Number of days at elevated level of care (ICU) through Day 28 after randomization
- Number of healthcare encounters through Day 28 after randomization

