6.1.7. Derived Variables

- Respiratory failure is defined as the requirement for use of intubation/mechanical ventilation, an oxygen rate with high flow nasal cannula greater than 20 L/min, non-invasive positive pressure respiratory support, or ECMO, or clinical diagnosis of respiratory failure.
- Respiratory failure-free survival is defined as the combination of no respiratory failure (defined above) and no report of mortality from any cause.
- Mortality from any cause is defined as death listed on the Study Completion CRF or WHO 9-point ordinal scale assessment of death.
- Non-invasive positive pressure respiratory support is defined as the use of continuous positive airway pressure (CPAP) or bilevel positive airway pressure (BiPAP).
- Ventilator use is defined as the use of mechanical ventilation, CPAP, or BiPAP.
- Organ failure is defined as a reported AE indicating a ‘failure’ of respiratory, cardiovascular, hepatic, renal, coagulation, or neurological reported at the PT level or

‘insufficiency’ reported as the lowest level term.

- Renal stabilization or replacement is defined as reported use of any type of dialysis in concomitant medications with a route recorded as (“HEMODIALYSIS”, “PERITONEAL DIALYSIS”, or “DIALYSIS”).
- Time to initiation of supplemental oxygen or other respiratory support in the first 28 days after randomization = (the earliest of Day 28 or date/time of the first use – date/time of randomization) + 1.
- Duration of supplemental oxygen or other respiratory support in the first 28 days after randomization = (the earliest of Day 28 of the study or date/time of the last use – the latest of date/time of the first supplemental oxygen or other respiratory support or date/time of randomization) + 1.
- Time to initiation of intubation/mechanical ventilation, an oxygen rate with high flow nasal cannula greater than 20 L/min, non-invasive positive pressure respiratory support, ECMO in the first 28 days after randomization = (the earliest of Day 28 or date/time of the first support – date/time of randomization) + 1.
- Duration of intubation/mechanical ventilation, an oxygen rate with high flow nasal cannula greater than 20 L/min, non-invasive positive pressure respiratory support, or ECMO in the first 28 days after randomization = (the earliest of Day 28 of the study or date/time of the last specified respiratory support – the latest of date/time of the first specified respiratory support or randomization) + 1.

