8.2.11. Days Without Renal Stabilization

The number of days without renal stabilization from randomization through Day 28 will be summarized descriptively and analyzed using ANCOVA. The LS means will be presented along with the associated 95% CI within each treatment group. In comparing treatments, LS mean differences between treatments will be presented along with associated 95% CIs and p-values. In order to assign the worst total score for death, participants that die will have all days from randomization through day 28 treated as if they were on renal stabilization.

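### Renal replacement is found only through three dialysis routes on concomitant-medication records, so a survivor's hemofiltration or route-less therapy entry would score as free days

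*SAP*

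**What the plan says.** SAP 2.2.1.2 lists the secondary endpoint: "Number of days without renal stabilization and/or replacement through Day 28 after randomization".

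SAP 6.1.7 supplies the derivation: "Renal stabilization or replacement is defined as reported use of any type of dialysis in concomitant medications with a route recorded as". Three values are accepted there, namely HEMODIALYSIS, PERITONEAL DIALYSIS and DIALYSIS. SAP 8.2.11 gives the analysis: "The number of days without renal stabilization from randomization through Day 28 will be summarized descriptively and analyzed using ANCOVA". For deaths it adds that "participants that die will have all days from randomization through day 28 treated as if they were on renal stabilization". Neither section names another data source.

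The protocol deals with dialysis as a therapy. Section 9.9.1, Prohibited Therapies, says "Dialysis before the study is prohibited" and goes on to mechanical ventilation and ECMO. Section 9.9 requires therapies to be captured as well as drugs: "concomitant therapies used will be recorded in the source document and on the appropriate eCRF".

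Renal replacement is also named in the WHO scale (Protocol Table 10-1, repeated in SAP 8.2.1), where score 7 reads "Ventilation plus additional organ support (pressors, renal replacement therapy (RRT), extracorporeal membrane oxygenation (ECMO".

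SAP Section 10 now reports Part 1 alone (18 participants), with summary statistics and confidence intervals for secondary outcomes and no P values.

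**The concern.** The endpoint's name covers renal replacement in general, but the derivation needs two things at once: a concomitant-medication record, and one of three route values on it. Renal replacement is a procedure. A site may enter it as a therapy with no route, or under a modality name such as hemofiltration. Either entry fails the rule, and an unmatched record is not flagged as missing. It is scored as no renal replacement.

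In survivors the error runs one way, since it can only add free days. What is at stake is the accuracy of one morbidity endpoint in arms so small that a single participant visibly moves the mean.

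**Working it through.** The plan gives no rate, duration or power figure for this endpoint, so there is no planned figure to reproduce. The check applies the rule as written and then measures the effect of one missed participant.

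**Inputs**
- Follow-up of 28 days, and the rule for deaths: SAP 8.2.11.
- The three accepted routes: SAP 6.1.7.
- Part 1 allocation 5:5:5:3 (n = 5 per active arm, n = 3 placebo); Part 2 planned as 72 participants at 1:1, so 72/2 = 36 per arm: SAP 3.2.
- Days of renal replacement d: not in the documents. I assume d = 7 and show 1 and 14 as a range.

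**Step 1: the rule as written**
- Death: score = 0.
- Survivor with a listed route: score = 28 − d.
- Survivor with any other route, or with no medication record: score = 28.

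**Step 2: a participant with d = 7**
- Survivor, route HEMODIALYSIS or DIALYSIS: 28 − 7 = 21.
- Survivor, hemofiltration under an unlisted route, or a therapy entry without a route: 28. Counting every modality would give 21, so the overstatement is 7 days.
- Death: 0 in every case, so the overstatement is 0.

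**Step 3: effect on an arm mean**
One missed survivor raises the mean by d/n.

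| Arm | d = 1 | d = 7 | d = 14 |
|---|---|---|---|
| Part 1 active, n = 5 | 1/5 = 0.20 | 7/5 = 1.40 | 14/5 = 2.80 |
| Part 1 placebo, n = 3 | 1/3 = 0.33 | 7/3 = 2.33 | 14/3 = 4.67 |
| Part 2 as planned, n = 36 | 1/36 = 0.03 | 7/36 = 0.19 | 14/36 = 0.39 |

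As an example, suppose all five participants in an active arm survive and one has 7 unmatched days. The rule reports a mean of 28. Counting all modalities gives (4 × 28 + 21)/5 = 26.6, which is 1.4 lower.

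**Step 4: does another rule rescue the record?**
- SAP 6.1.4 derives missing data from contemporaneous clinical data. An unmatched entry is not missing under the definition, so that rule does not apply.
- SAP 6.1.7 takes mortality from either the Study Completion CRF or the WHO scale. Renal replacement has no such second source.

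**The case against.** The strongest reply is that the failure depends on an eCRF that the documents do not show. The Schedule of Events has one row for concomitant medications and therapies together, which fits a single form. The SAP says it was written with sample data collection documents to hand, and the three capitalised values look like actual database entries. If the form forces every modality into them, nothing is missed. This stands as a limit on frequency: the documents do not show that any record will be missed. They do not show that the form closes the gap either, and the SAP does not say so.

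The definition also opens with any type of dialysis and accepts the generic value DIALYSIS. This stands too. A reader might infer that continuous renal replacement is always lost, but when entered as a medication with that route it is counted.

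A reader might also infer that WHO score 7 already identifies the missed days. It does not. The score pools pressors, renal replacement and ECMO, and it requires ventilation. It can prompt a question but cannot supply renal replacement days.

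A further tempting reading is that a renal safety difference would be hidden. The documents do not support it. Creatinine, BUN and eGFR are collected (Protocol 10.3.3.1.1), laboratory results get shift tables (SAP 9.2), AEs are tabulated (SAP 9.1), and all collected data are listed (SAP 6.1.8).

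Finally, the weight is low. This is one of 13 secondary endpoints and not among the four key ones in SAP 8.1.1. Entry excludes eGFR below 60 mL/min, and Part 1 efficacy carries no hypothesis test. All of that stands and sets the grade.

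**Conclusion.** The point holds as a minor defect in a derivation rule. For survivors, renal replacement recorded without one of the three routes on a medication record is scored as days without it. Participants who die are unaffected.

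The size rests on an assumed duration. With 7 missed days in one survivor, the shift is 1.4 days in a 5-person Part 1 arm and 2.33 days in the 3-person placebo arm. Both would appear in the descriptive Part 1 summaries. In a 36-person Part 2 arm it would be 0.19 days, but recruitment paused with one Part 2 participant, so that figure describes the plan and not current reporting. How often a record would be missed is unknown.

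A bias between arms should not be inferred. Recording is done by blinded staff, and nothing in the documents makes unmatched entries likelier in one arm.

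**What to change.** In SAP 6.1.7, count a renal replacement day from any concomitant medication, therapy or procedure record whose term, indication or route denotes dialysis, hemofiltration, hemodiafiltration or other continuous renal replacement. Use WHO score 7 only to trigger a blinded query before lock about which organ support was given, not as a source of renal replacement days. If the eCRF does place every modality under the three routes, one sentence in 6.1.7 saying so would close the point.

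The cost is revised wording, a wider term search and a few queries, with no new assessments. SAP Section 10 says its changes precede the Part 1 database lock and that a protocol and SAP amendment is to follow for Part 2, so the wording can go in at either step.

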#### 8.2.2 Exclusion Criteria

A participant will be excluded from the study if he or she meets any of the following criteria:

1. Participant has mild, moderate, or critical COVID-19 defined in accordance with the FDA Guidance for Industry:

- a. Mild COVID-19:
  - i. Symptoms of mild illness with COVID-19 that could include fever, cough, sore throat, malaise, headache, muscle pain, gastrointestinal symptoms, without shortness of breath or dyspnea
  - ii. No clinical signs indicative of moderate, severe, or critical severity
- b. Moderate COVID-19:
  - i. Symptoms of moderate illness with COVID-19, which could include any symptom of mild illness (fever, cough, sore throat, malaise, headache, muscle pain, gastrointestinal symptoms) or shortness of breath with exertion
  - ii. Clinical signs suggestive of moderate illness with COVID-19, such as respiratory rate  $\geq 20$  breaths per minute, peripheral oxygen saturation ( $\text{SpO}_2$ )  $> 93\%$  on room air at sea level, heart rate  $\geq 90$  beats per minute
  - iii. No clinical signs indicative of severe or critical illness
- c. Critical COVID-19:
  - i. Respiratory failure defined based on resource utilization requiring at least one of the following:
    - Endotracheal intubation and mechanical ventilation
    - Oxygen delivered by high-flow nasal cannula ([HFNC] heated, humidified, oxygen delivered via reinforced nasal cannula at flow rates  $> 20$  L/min with fraction of delivered oxygen  $\geq 0.5$ )
    - Noninvasive positive pressure ventilation
    - ECMO, or
    - Clinical diagnosis of respiratory failure (i.e., clinical need for one of the preceding therapies, but preceding therapies not able to be administered in setting of resource limitation)
  - ii. Shock (defined by systolic blood pressure  $< 90$  mmHg, or diastolic blood pressure  $< 60$  mmHg or requiring vasopressors)
  - iii. Multi-organ dysfunction/failure

2. Participant has taken investigational medications within 7 days or 5 half-lives prior to enrollment, whichever is shorter.
3. Participant has required any new form of sedation, anxiolysis or central nervous system (CNS) depressant within the 48 hours prior to enrollment that would interfere with neurologic assessments at enrollment.
4. Has history of cerebrovascular accident or intracranial bleeding of any kind, acute coronary syndrome, myocardial infarction, or severe pulmonary hypertension.

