5. Participant has chronic respiratory failure not associated with COVID-19, defined as prior need for home oxygen, need for home noninvasive positive-pressure ventilation (NIPPV) for reasons other than isolated sleep apnea, or other signs of chronic respiratory failure, in the investigator's judgment.
6. Upper gastrointestinal (GI) bleed evidenced by hematemesis, "coffee-ground" emesis or nasogastric aspirate, or hematochezia thought to originate from upper GI tract.

7. Participant has abnormal liver function defined as any 2 of the following at screening:
  - a. Total bilirubin  $\geq 2 \times$  ULN
  - b. Alanine aminotransferase (ALT)  $\geq 3 \times$  ULN
  - c. Aspartate aminotransferase (AST)  $\geq 3 \times$  ULN
  - d. Alkaline phosphatase (ALP)  $> 3 \times$  ULN
  - e. Gamma-glutamyl transferase (GGT)  $> 3 \times$  ULN
8. Participant has an estimated glomerular filtration rate (eGFR)  $< 60$  mL/min.
9. Participant has a known allergy or significant adverse reaction to varespladib-methyl or related compounds.
10. Participant is considered by the investigator to be unable to comply with protocol requirements due to geographic considerations, psychiatric disorders, or other compliance concerns; or has any serious medical condition or clinically significant laboratory, ECG, vital sign, or physical examination abnormality that would prevent study participation or place the participant at significant risk, as judged by the Investigator.
11. Participant is breast-feeding, pregnant, has a positive serum hCG pregnancy test, or is not willing to use a highly effective method of contraception for 14 days after treatment.  
Highly effective methods of contraception are as follows:
  - a. Combined (estrogen- and progestogen-containing) hormonal contraception associated with inhibition of ovulation (oral, intravaginal, or transdermal)
  - b. Progestogen-only hormonal contraception associated with inhibition of ovulation (oral, injectable, or implantable)
  - c. Intrauterine device, intrauterine hormone-releasing system
  - d. Bilateral tubal occlusion
  - e. Vasectomized partner
  - f. Sexual abstinence
  - g. Double-barrier method (condoms, sponge, diaphragm, with spermicidal jellies, or cream)

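### SAP 6.1.7 counts breaks in respiratory support as support days and gives no valid oxygen initiation time for participants already on oxygen at randomization

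*SAP*

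**What the plan says.** **Duration (SAP 6.1.7).** For oxygen or other support, the end point is "the earliest of Day 28 of the study or date/time of the last use" and the start point is "the latest of date/time of the first supplemental oxygen or other respiratory support or date/time of randomization"; the difference plus 1 is the duration. Critical-level support follows the same pattern and ends at "the earliest of Day 28 of the study or date/time of the last specified respiratory support". Neither formula deducts time off support. SAP 8.2.4 and 8.2.5 describe the analysed quantity as a number of days of support and refer to 6.1.7 for its calculation. SAP 8.2.12, days of oxygen support, has no formula.

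**Initiation (SAP 6.1.7).** The oxygen formula uses "the earliest of Day 28 or date/time of the first use" and the critical-support formula uses "the earliest of Day 28 or date/time of the first support", each minus randomization, plus 1. Neither is floored at randomization, unlike the duration formulas.

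**Oxygen at entry (Protocol 8.2.2).** Exclusion 5 concerns chronic respiratory failure, "defined as prior need for home oxygen" among other signs. Exclusion 1.c.i lists critical-level support only. Its high-flow item requires a flow above 20 "L/min with fraction of delivered oxygen" of at least 0.5. SAP 6.1.7 instead uses "an oxygen rate with high flow nasal cannula greater than 20 L/min", with no condition on the oxygen fraction. Protocol 7.2 states that patients already needing oxygen are excluded, but no criterion does this. Protocol 5.1 describes severe disease, the population enrolled, as needing oxygen.

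**Part 1 reporting (SAP Section 10).** Part 1 secondary outcomes, previously to be listed only, now also get summary statistics and confidence intervals. The subsetting in 8.2.4 and 8.2.5 is dropped, so all 18 Part 1 participants (5:5:5:3) enter both endpoints.

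**The concern.** The endpoint is described as a count of support days, but the formula returns the span from first to last use. The two agree only when support is unbroken. A participant who comes off oxygen and later needs it briefly again is scored as if supported throughout.

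For initiation, someone already on oxygen at randomization has no start to time, and the SAP has no rule for that case. The floor in the duration formula shows that the SAP foresees support begun before randomization.

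Both quantities serve the secondary objective on the need for respiratory support. With 5 or 3 participants per arm, one mis-derived value can visibly move an arm summary.

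**Working it through.** The plan states no figure to reproduce. The check applies the SAP 6.1.7 formulas literally, with Day 1 as the day of randomization. The histories below are illustrative, not taken from the documents.

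**1. Duration.** Formula: min(Day 28, last use) − max(first use, randomization) + 1. The excess over the count of support days equals the gap g. One such participant raises the arm mean by g/5 (active arm) or g/3 (placebo).

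| Days on support | Formula | Days counted | Gap g | g/5 | g/3 |
|---|---|---|---|---|---|
| 1–8, unbroken | 8 | 8 | 0 | 0 | 0 |
| 1–3 and 12–14 | 14 | 6 | 8 | 1.6 | 2.7 |
| 1–3 and 20–22 | 22 | 6 | 16 | 3.2 | 5.3 |
| 1 and 28 only (largest gap) | 28 | 2 | 26 | 5.2 | 8.7 |

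The smallest gap, 1 day, adds 1/5 = 0.2 or 1/3 = 0.3 days.

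**2. Oxygen initiation, literal reading.** Formula: min(Day 28, first use) − randomization + 1. Oxygen started h hours before randomization gives 1 − h/24:

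- h = 12: 0.5
- h = 24: 0
- h = 48: −1
- h = 72: −2

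Compared with a value of 1, the last three differ by 1, 2 and 3 days. Each such participant lowers the arm mean by 0.2, 0.4 or 0.6 days (n = 5), or by 0.3, 0.7 or 1.0 days (n = 3).

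**3. Oxygen initiation, read as first use after randomization.** Everyone on oxygen at entry gets about 0 + 1 = 1, and all other values are at least 1. The arm median is therefore 1 once 3 of 5 or 2 of 3 are on oxygen at entry. Kaplan-Meier gives the same result: survival just after time 1 is at most 1 − 3/5 = 0.40 or 1 − 2/3 = 0.33, both below 0.5. The median then reflects oxygen use at entry, not when oxygen was started.

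**4. Critical-support initiation.** Exclusion 1.c.i excludes high-flow oxygen above 20 L/min only when the delivered fraction is at least 0.5. The SAP definition has no fraction condition. A participant above 20 L/min with a lower fraction can pass that exclusion item and already meet the SAP definition at randomization. The same missing floor then applies.

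**5. Do other rules repair this?** SAP 6.1.4 assigns an appropriate value to participants without the event and carries the last value forward for missing data. SAP 8.2.4 and 8.2.5 set values for deaths. None of these covers survivors with breaks in support or participants on oxygen at entry.

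**The case against.** **A span can be a legitimate duration.** The endpoint list has duration of support and, separately, number of days of oxygen support (8.2.12), so a span and a count could coexist. With subsetting removed, counting days in both would make 8.2.4 and 8.2.12 nearly the same quantity in Part 1. That overlap is real. However, 8.2.4 and 8.2.5 call the result a number of days, and 8.2.5 assigns deaths 28 days of support. For critical-level support there is also no separate day-count endpoint. If the span is kept and 8.2.12 is counted by day, two Part 1 tables could disagree on almost the same quantity.

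**The negative times rest on the less likely reading.** The variable's title refers to the first 28 days after randomization, which favours first use after randomization. In addition, 8.2.4 specifies Cox and Kaplan-Meier methods for initiation, so a mean arises only if Section 10's general rule for continuous outcomes is applied. Both points stand. The duration floor supports the literal reading, though, and the other reading gives a constant of about 1.

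**The number affected is unknown.** Inclusion 1 can be met on respiratory or heart rate, and Protocol 7.2, which may partly mean home oxygen, says patients on oxygen are excluded. It stands that no frequency can be given. The 8- and 16-day gaps are assumed, and gaps of 1 to 2 days move an arm mean by only 0.2 to 0.7 days.

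**The high-flow wording may be shorthand.** SAP 8.2.3 cites exclusion 1.c.i beside the same wording. That is possible, but the definition in 6.1.7 does not say so.

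**Lasting impact is small.** Part 1 has no efficacy p-values, all data are listed, and Section 10 already plans an amendment on these endpoints for Part 2. This limits the weight of the point, but that amendment does not cover Part 1.

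**Conclusion.** The concern holds. The duration rule is wrong as written for any survivor with a break in support, and correct for unbroken support. The oxygen initiation rule gives no usable value for participants already on oxygen at randomization, under either reading. The critical-support initiation rule has the same gap, but only for a participant on high-flow oxygen that the SAP counts and exclusion 1.c.i does not.

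A single break of 1 to 26 days adds 0.2 to 5.2 days to the mean of an arm of 5, or 0.3 to 8.7 days with 3 participants. These sizes assume one affected participant per arm. The documents give neither the frequency of breaks nor the share on oxygen at entry. The effect is limited to descriptive Part 1 secondary summaries and their confidence intervals; these duration and initiation formulas do not enter the primary endpoint. The change should be made, but the trial's main result does not depend on it.

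**What to change.** Before Part 1 database lock:

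1. Define both durations as the count of days with recorded support from randomization through Day 28, and state the same counting rule for 8.2.12. If support is recorded only as episodes, sum the episode lengths and count overlapping days once. Leave the existing assignments for deaths unchanged.
2. Report how many participants are on oxygen at randomization. Summarize oxygen initiation among those not on it, stated as an explicit baseline-defined exception to Section 10's all-ITT rule, and keep all participants in the listing. A floor at randomization is not enough, because it gives 1 to everyone already on oxygen.
3. For critical-support initiation, report and list separately anyone who already meets the SAP definition at randomization. Reconcile the high-flow wording of SAP 6.1.7 with exclusion 1.c.i.
4. Reconcile Protocol 7.2 with the entry criteria on oxygen at entry.

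The cost is SAP wording and programming. SAP 6.1.7 already needs first-use and last-use times, and Protocol 10.3.1.1 has oxygen need assessed throughout. The case report form is not in the documents, so whether support is recorded by day or by episode must be checked; either would serve. The count should rest on the support records, because the schedule has no WHO-scale assessment between Days 21 and 28. The real drawback is that the baseline exception departs from all-ITT and may leave few participants, so a count and a listing may be all that Part 1 supports for initiation.
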